## PROJECT TITLE:

Effectiveness of Electrical Neurostimulation as an Opioid-Sparing Alternative in the Treatment of Cyclic Vomiting Syndrome.

PI NAME	[name]	
CO-PI NAME(s)	[name]	
Co-Investigators	[name] [name]	

NCT#: NCT04721171

Document Date: 02/18/2019

Cyclic vomiting syndrome (CVS) is a chronic functional gastrointestinal disorder (FGID) characterized by episodic nausea, vomiting and severe abdominal pain in majority (80%) of patients. Most patients also have a migraine headache, photophobia, phonophobia and lethargy during an episode. The pathophysiology of CVS is not known but is thought to be a migraine diathesis given the overlap between the two syndromes. Various factors such as mitochondrial DNA polymorphisms, genetic variants in the cannabinoid receptor genes and and calcitonin gene-related peptide (CGRP) are thought to play key roles.

CVS is common and affects 2% of the population in the US. The disorder is disabling, and healthcare costs associated with CVS hospitalizations in adults are staggering, amounting to \$200 million dollars bi-annually. Due to sub-optimal therapies, hospitalized patients are usually treated empirically with IV fluids, anti-emetics, benzodiazepines and opioids for the intense abdominal pain. Unfortunately, opiate therapy in CVS is fraught with problems and is a risk factor for recurrent hospitalizations (preliminary data) as well as non-response to prophylactic therapy. Additionally, use of opioids is associated with dependence, withdrawal, addiction, overdose and even death. Hence, there is a critical need for safe, opiate-sparing strategies to treat pain associated with CVS episodes. Neurostimulation via a novel auricular percutaneous electrical nerve field stimulation (PENFS) device has recently emerged as a safe and non-invasive therapy for the treatment of pain, nausea and vomiting disorders. This therapy was recently FDA-approved for the symptoms of opioid withdrawal. Preliminary data indicates that PENFS modulates peripheral vagal nerve signaling, likely also modulating the trigeminal pathway from the external ear to the brainstem.

We hypothesize that 1) **PENFS** is a safe, non-invasive opioid-sparing alternative therapy for the severe abdominal pain, nausea and vomiting associated with CVS. We also hypothesize that 2) PENFS reduces length of stay (LOS), and improves patient satisfaction. We propose the following specific aim:

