## Opioid use in CVS and the critical need for opioid sparing therapy

Given the lack of knowledge about pathophysiology and evidence-based therapies, patients are often hospitalized to treat symptoms of CVS. During an episode, patients present with severe vomiting and abdominal pain and are treated empirically with IV fluids, antiemetics, benzodiazepines, and opioids. Estimates of opioid use range from 23%-27% in adults with CVS. Patients are often dissatisfied with the level of analgesia as recurrent opioid use results in tolerance and dependence. This often undermines the physician-patient relationship and patients even leave against medical advice out of frustration with what they perceive as ineffective care. This can lead to worse outcomes including recurrent hospitalizations, morbidity and increased health care costs.

Preliminary data from a study by our group reveals that of 101 patients hospitalized with CVS at Froedtert Hospital, chronic opioid therapy is associated with a two-fold increased risk of hospitalization (RR 2.22, CI 1.1-4.4, P=0.02) and three-fold increase in hospital length of stay (LOS) (RR 3.43, CI 1.26-9.34, P=0.01). In a study of 132 CVS patients, opioid use was associated with non-response to amitriptyline (53% vs 15%, p<0.05), a prophylactic therapy used in CVS. In turn was associated with increased frequency and duration of CVS episodes per year and increased number of hospitalizations/emergency

department (ED) visits at baseline (18% vs 15.2%, p<0.05). Hence there is an urgent need for an opioid-sparing, non-invasive strategy to treat CVS symptoms.

In summary, CVS is common and disabling and is associated with significant health care costs. Much of this burden can be tied to iatrogenic opioid overuse, resulting in chronic opioid use and high risk of addiction and health care utilization. Understanding the pathophysiology of CVS and development of novel therapies are urgently needed. Further, similar to other disorders with rampant opioid use, **there is a critical need for opioid-sparing therapy in CVS to negate the devastating short and long-term effects of opioid use**. Our proposed project using a novel, non-invasive device to treat CVS will also address the current opioid crisis.

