## (C) Approach, Feasibility, and Environment

## Aim 1: Investigate the efficacy of PENFS in adults admitted with cyclic vomiting syndrome

## Methods

**Inclusion/Exclusion Criteria.** We will enroll 80 adults between the ages of 18-65 years with a diagnosis of CVS (based on Rome IV diagnostic criteria). This study will only include patients who are admitted to Froedtert Hospital with an episode of CVS. Exclusion

criteria includes developmental delays, non-English speaking patients, pregnancy, any implanted electrical device or any significant dermatological/infectious condition of the ear.

Randomization. Subjects will be randomized to the intervention group (receiving the Bridge device) or control group (receiving an identical sham device lacking electrical charge) in 1:1 ratio. The auricular neurostimulator device will be placed on the subject's ear upon presentation to the hospital. The device delivers low voltage (3.2), continuous stimulation for 5 days (around the clock) in alternating frequencies (1-10Hz) with an impulse interval of 100ms/2 sec. The neurostimulators (for both treatment arms) will be placed by a certified MD/APP/RN inside the patient's room. All patients will be allowed to receive rescue medications after implantation of the device if the symptoms do not improve with the device or at patient's request.

We have performed a sample size calculation based on prior data. At a significance level of 0.05 and 80% power, we estimate a sample size of 40 participants per group to detect the minimum standardized effect size of 0.64 using two-sided tests, using prior data. We will compare the different variables (average daily reduction in abdominal pain, nausea/vomiting scores, average daily use/frequency/dosage of rescue medications (opiates, antiemetics and sedatives between PENFS vs sham device.

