Outcomes. Primary outcome will include the change in abdominal pain and concurrent opioid use. Abdominal pain will be assessed daily through Visual Analog Scale with the score ranging from 0 to 10, with 0 being the least and 10 being the worst pain. The need for opiates will be assessed through- (a) the time taken by the subject from the time of admission to the first felt need accompanied by the actual administration of opiates (IV hydromorphone or morphine), (b) daily frequency and total dosage of opiates received. Secondary outcomes will include- (a) severity of daily nausea and vomiting assessed through the Index for Nausea, Vomiting and Retching (INVR); (b) the need for other rescue medications (which include antiemetics like ondansetron, promethazine & metoclopramide; benzodiazepines like lorazepam; antihistaminics like diphenhydramine, etc.), (c) hospital LOS and (d) survey on patient satisfaction. While all other outcomes will be assessed daily, LOS and patient satisfaction will be assessed at the time of discharge (Table 1). All variables will be compared between the subjects in intervention arm versus control arm.

We hypothesize that PENFS will effectively mitigate the abdominal pain, nausea and vomiting associated with CVS episodes, obviate or reduce the need for opiates and simultaneously improve healthcare outcomes including LOS and patient satisfaction.

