**Table 1. Study Protocol** 

Tubic 1. Study	1100001					
	Admission (0 hours)	2 hours post - placement	24 hrs.	Daily	5 days*	Discharge
Screening & Consent	X					

Demographics	X					
Neurostimulator (PENFS) vs sham	X	X	X	X	X	
Rome IV questionnaire 	X					
INVR (vomiting scale; daily during therapy) 	X	X	X	X	X	X
Abdominal pain (Visual Analogue Scale)	X	X	X	X	X	X
Need for opiates and other rescue medications	X	X	X	X	X	X
Length of stay						X
Patient Satisfaction Survey						X

INVR=Rhodes Index of Nausea, Vomiting & Retching; CGRP= Calcitonin Gene-Related Peptide

**Statistical Analysis:** Summary statistics, such as mean, median, standard deviation and range will be used as a first step to examine data. To satisfy parametric assumptions, we may perform transformations with justifications if possible and otherwise use non-parametric tests. For any binary outcomes, we will use Chi-square or Fisher's exact tests to compare the proportions between the two groups. We will compare the different variables (average daily reduction in abdominal pain, nausea/vomiting scores, average daily use/frequency/dosage of rescue medications (opiates, antiemetics and sedatives) between PENFS vs sham device. Data analyses will be performed using SAS version 9.4 (SAS institute, Cary, NC).

**Potential Pitfalls:** This pilot data is both safe and non-invasive and will help us better understand the pathophysiology underlying CVS symptoms. The proposed device is non-invasive and currently utilized at our institution. The PI is certified in the PENFS placement and has already used it in some of her patients with success. We thus expect no feasibility or safety issues. Potential risks generally would include bleeding or infection at the puncture site, pain at the application site, or skin irritation at the site of application.

**Feasibility**: Recruitment should not pose a problem as the PI ([name]) has the largest cohort of patients with CVS in the nation. Further in our experience, CVS sufferers are also highly motivated to enroll in studies and trial new therapies The PI also works closely with the Cyclic Vomiting Syndrome Association, who will advertise the study on their website and

\* questionnaires will be completed as an outpatient if patient is already discharged

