## (D) Special Emphasis

Patients who are admitted to the hospital with a CVS episode typically suffer from intense abdominal pain. Opiates with anxiolytic properties are therefore particularly effective in controlling symptoms in patients with CVS. Consequently, patients admitted with a CVS episode frequently require treatment with intravenous opioids. The addictive potential of narcotic pain medications is well known. As with other acute painful conditions, the use of opioids during a CVS episode may be followed by ongoing use of opioids. Also, withdrawal from opiates may be equivalent to a panic trigger for another exacerbation for a CVS episode. Therefore, patients are often reluctant to give up using opiates on an ongoing basis. Ongoing use of opioids in turn leads to disease coalescence with opioid dependence and withdrawal leading to recurrent episodes of CVS exacerbation. Escalating use of opiates can also lead to narcotic bowel syndrome which is characterized by worsening bouts of abdominal pain induced by opioid-induced bowel dysfunction.

The main focus of our study is to replace the need for intravenous opiates during a CVS episode with a non-invasive and safe device that can be placed with ease and does not require specific expertise.

- 7. Sunku B, Li BUK . Cyclic vomiting syndrome. In: Guandalini S, editor. Textbook of Pediatric Gastroenterology and Nutrition. London, United Kingdom: Taylor and Francis Group; 2004. pp. 289–302.

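### Time to first opioid runs from admission rather than from the start of treatment, and no rule covers an opioid given in between

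*Combined protocol and SAP*

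**What the plan says.** In the Outcomes paragraph under Methods, the primary outcome combines change in abdominal pain with opioid use. Opioid need is measured in two ways. Item (a) is "the time taken by the subject from the time of admission to the first felt need accompanied by the actual administration of opiates", the drugs being IV hydromorphone or morphine. Item (b) is daily frequency and total dose, with no start time stated.

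On eligibility, Methods says: "This study will only include patients who are admitted to Froedtert Hospital with an episode of CVS". On the start of treatment: "The auricular neurostimulator device will be placed on the subject's ear upon presentation to the hospital". Certified staff place the device in the patient's room. Table 1 puts consent, demographics, Rome IV, baseline pain and INVR scores and the device all in the 0-hour admission column. The next column is "2 hours post - placement".

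The only rescue rule is "All patients will be allowed to receive rescue medications after implantation of the device if the symptoms do not improve with the device", or if the patient asks. The exclusion criteria do not mention opioids already received.

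On usual care, the project summary says "hospitalized patients are usually treated empirically with IV fluids, anti-emetics, benzodiazepines and opioids for the intense abdominal pain". The section on opioid use in CVS says "patients present with severe vomiting and abdominal pain and are treated empirically with IV fluids, antiemetics, benzodiazepines, and opioids". Special Emphasis says "patients admitted with a CVS episode frequently require treatment with intravenous opioids".

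**The concern.** The clock for item (a) starts before the treatment it is meant to evaluate. Only admitted patients are eligible, and consent, the Rome IV questionnaire, baseline scores and randomization must all come before the device is fitted. Some interval is therefore unavoidable, in patients who arrive vomiting and in severe pain. The plan puts no limit on it and does not say how an opioid given within it is handled.

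A dose given on felt need in that interval meets the definition in item (a) and becomes the patient's event, before any active or sham device is on. Such an event carries no information about the device. Reducing the need for opioids is objective 1b, and Special Emphasis calls replacing IV opiates the main focus of the study, so this measure should not be weakened by its own definition.

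**Working it through.** **The plan's own figure.** Inputs from Methods: standardized effect 0.64, two-sided 0.05, 80% power. Normal approximation: n = 2 × (1.96 + 0.8416)² / 0.64² = 2 × 7.849 / 0.4096 = 38.3, so 39 per group. The t-test version gives 39.3, rounded up to 40, with 80.7% power at 40 per group. The stated 40 per group reproduces and is not in dispute. It is not based on time to first opioid, for which the plan gives no assumption and names no test.

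**What the documents do not supply.** They give neither the delay from admission to placement nor the share of patients dosed during it. Everything below is illustration under assumption. The log-rank test is my choice.

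**Hand calculation.** Suppose all 80 patients have an event and the hazard ratio is the one that gives 80% power by Schoenfeld's formula: exp(−2.8016 / √20) = 0.534. If a share f of each arm is dosed before treatment, those events add variance but no signal. The expected test statistic shrinks from 2.80 to 2.80 × (1 − f), and power is Φ(2.80 × (1 − f) − 1.96):

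- f = 10%: Φ(0.56) = 71%
- f = 20%: Φ(0.28) = 61%
- f = 30%: Φ(0.00) = 50%
- f = 50%: Φ(−0.56) = 29%

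A simulation with the same hazard ratio (6000 trials per cell, 2 h gap, sham mean 12 h to first opioid after placement) starts at 77% with f = 0. With the admission clock it falls to 68%, 56%, 45% and 24% at these four shares. With the clock at placement it stays at about 78%, provided an early dose neither predicts the next one nor alters the device effect.

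**Allowing for patients who never need an opioid.** A second simulation used 40 per arm, 4000 trials per cell and 120 h of follow-up after placement. Sham 5-day risks of 50%, 80% and 95% were paired with hazard ratios 0.34, 0.46 and 0.51, chosen to give about 80% power without early dosing (78.6%, 80.7%, 80.6%). Early doses fell uniformly in a gap of 2 to 6 h. Ranges run over these settings.

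| Share of each arm dosed early | 5% (2 of 40) | 10% (4 of 40) | 25% (10 of 40) |
|---|---|---|---|
| Admission clock | 70.5%-75.7% | 60.7%-70.6% | 39.2%-53.1% |
| Placement clock, stratified; early dose does not predict the next | 78.6%-80.7% | 78.5%-79.1% | 76.8%-80.2% |
| Placement clock, stratified; later hazard doubled after an early dose | 79.1%-80.1% | 79.4%-80.3% | 80.3%-84.6% |
| Placement clock, stratified; every early-dosed patient redosed within 6 h regardless of device | 73.7%-76.3% | 67.3%-72.1% | 42.5%-54.4% |

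In the last scenario the admission clock gives 70.5%-75.1%, 62.6%-69.9% and 39.2%-52.2% in the same trials, so moving the clock recovers only about 1 to 5 points. The placement-clock rows stand in for a clock started at randomization if randomization comes immediately before placement.

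**A ceiling that follows directly.** With the admission clock, the share of patients who could be counted as needing no opioid is at most 95%, 90% or 75% at these three shares, however well the device works.

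**The case against.** The strongest reply is that the plan intends one time zero. The device goes on at presentation, Table 1 lists it at 0 hours, and rescue is mentioned only after placement. On that reading the gap is near zero and this is an unstated edge case. The intent is clear and stands. But intent does not settle the definition: no sentence equates admission with placement, and the rescue sentence permits later dosing without forbidding or classifying an earlier dose.

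Second, item (a) requires a felt need as well as an administration. A purely empirical dose does not clearly meet it, so a reader should not infer that every early opioid would count. This stands; the point is limited to doses given on felt need.

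Third, a reader might infer from the background sections that patients in this trial will be dosed before placement. Those sections describe usual care. Early dosing is plausible from them, but they give no rate. The only opioid-use figure, 23%-27% of adults with CVS in the section on opioid use, is not a rate before placement and may not describe inpatients. If it were the sham risk, the same hazard ratios would give only about 25%-51% power with no early dosing at all. A fall from 80% is therefore not a property of this trial.

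Fourth, the consequence is confined. Item (b) still captures later doses, and the comparison lists in Methods and Statistical Analysis name daily use, frequency and dosage rather than time to first opioid, although the Outcomes paragraph says all variables will be compared. This limits the weight of the point but does not remove it.

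**Conclusion.** The point holds as a defect in the definition of one component of the primary outcome. The origin of item (a) precedes treatment, and no rule covers an opioid given in between. Any dose on felt need in that interval would be an event in either arm that the device could not affect.

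The effect is dilution and lost power. A reader might infer that the comparison is biased for or against the device. The documents do not support that: allocation is randomized, the sham looks identical, and nothing suggests that dosing before the device is on would differ by arm. VAS pain is unaffected.

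The size is unknown. It is zero if nobody is dosed early. The illustrations, a few points lost at 5% dosed early and roughly 25 to 40 points at 25%, rest on assumed shares, gaps, sham risks, hazard ratios and a test the plan does not name.

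**What to change.** 1. Redefine item (a) as time from randomization to the first IV hydromorphone or morphine dose afterwards, for all randomized patients, fitted or not. Randomize immediately before placement and after consent, Rome IV and baseline VAS and INVR, and state that order for the 0-hour column of Table 1. Keep the instruction to fit the device promptly. Use the same start for frequency and dose in item (b).
2. Record any opioid given from presentation up to randomization, including before admission, as a baseline variable (yes or no, dose, time). Adjust or stratify for it and keep these patients in the analysis. A dose after randomization but before placement counts as an event; treating it as baseline would weaken the comparison as randomized.
3. Report pre-randomization opioids descriptively by arm.

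The cost is a few sentences in Methods and Table 1, a recorded randomization time and one baseline variable. Dosing times are already needed for item (a). No patients or visits are added. There are two downsides: the outcome no longer covers opioids given before randomization, and little power returns if early-dosed patients are redosed regardless of the device. Any power figures quoted in support should be labelled as illustrations under assumption.

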# Aim 1. Investigate the efficacy of PENFS compared to a sham in hospitalized patients with CVS

## **Objective 1:**

- a. Demonstrate reduction in abdominal pain, nausea and vomiting using validated tools.
- b. Obviate or reduce the need for opioids.
- c. Reduce length of hospital stay and improve patient satisfaction.

This approach will specifically address the current opioid problem using a novel, non-invasive neurostimulation therapy with proven efficacy for opioid withdrawal. Long-term, it may improve health care outcomes and significantly reduce overall health care costs.

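### Length of stay is compared without regard to type of discharge, so unequal self-discharge would favour the arm that has more of it

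*Combined protocol and SAP*

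**What the plan says.** All references are to the combined protocol and SAP.

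- Objective 1, item c, sets the direction of benefit: "Reduce length of hospital stay and improve patient satisfaction". The second hypothesis in the opening section says the same.
- The Outcomes paragraph under Methods lists among the secondary outcomes "c) hospital LOS and (d) survey on patient satisfaction". It adds that "LOS and patient satisfaction will be assessed at the time of discharge" and that "All variables will be compared between the subjects in intervention arm versus control arm".
- The Statistical Analysis paragraph below Table 1 offers summary statistics, chi-square or Fisher tests for binary outcomes, and for the rest: "we may perform transformations with justifications if possible and otherwise use non-parametric tests". Its list of variables to be compared does not name LOS.
- Table 1 has one LOS entry, at discharge. Its footnote on patients who have already gone home concerns questionnaires only.
- The background section on opioid use in CVS says that "patients even leave against medical advice out of frustration with what they perceive as ineffective care", and links this to worse outcomes, including repeat admissions.

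No section defines the start or end of LOS, records the type of discharge, or says how an exit against advice is handled. The phrase 'raw time to discharge' is not in the plan, but it is the natural reading of LOS taken at discharge and compared between arms with no further rule.

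**The concern.** The plan describes self-discharge as something that follows perceived treatment failure. It then uses an endpoint on which a self-discharge looks like a good result, because the stay is short. Self-discharge happens after randomisation and may depend on how well symptoms are controlled, which is what the device is meant to change. Randomisation therefore does not guarantee that it is balanced.

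If sham patients leave against advice more often, sham LOS is shortened and a real benefit of the device is partly hidden. If active patients leave more often, the device gains a shorter stay that it has not earned. Without a record of discharge type, nobody could tell afterwards which had happened. The section on future plans says the results are meant to support a larger multicentre proposal, so a distorted LOS estimate could be carried into that design.

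**Working it through.** **The plan's own figure.** The Methods section sets its conditions as "At a significance level of 0.05 and 80% power" and a "minimum standardized effect size of 0.64 using two-sided tests", with 40 per group. A two-sample t-test calculation gives 39.3, rounded up to 40 per group, and 80.7% power at 40. The figure reproduces. The plan does not tie it to LOS, and it does not depend on how self-discharge is handled.

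**Inputs for LOS**

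- From the documents: 40 per arm, two-sided 0.05.
- Assumed, because the documents give no LOS mean or SD and no self-discharge rate: log-normal LOS with log-SD 0.6 (the median cancels on the log scale); true ratio of active to sham *R* = 0.7, a 30% reduction; self-discharge proportions *qA* (active) and *qS* (sham); exit at a fraction *f* of the stay otherwise needed, with *f* = 0.5 or 0.75; t-test on log LOS.

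**Formulas**

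- Observed ratio of geometric means = *R* × *f*^(*qA* − *qS*).
- Variance of log LOS in an arm = 0.36 + *q*(1 − *q*)(ln *f*)².
- Standard error = √[(*VA* + *VS*)/40].

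**One row in full: 15% sham, 5% active, *f* = 0.5**

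- Observed ratio = 0.7 × 0.5^(−0.10) = 0.750, a 25% reduction in place of 30%.
- *VA* = 0.36 + 0.05 × 0.95 × 0.4805 = 0.3828.
- *VS* = 0.36 + 0.15 × 0.85 × 0.4805 = 0.4213.
- Standard error = √(0.8041/40) = 0.1418.
- |ln 0.750|/0.1418 = 0.2874/0.1418 = 2.03. Power is about Φ(2.03 − 1.96) = 53%, or 52% with the t distribution.

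**Range.** Reductions come from the formula and powers from simulation. The formula with the t distribution agrees with the simulated powers to within about one percentage point.

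| Sham vs active self-discharge | Observed reduction (*f* = 0.5 to 0.75) | Power (*f* = 0.5 to 0.75) |
|---|---|---|
| none | 30% | about 74% |
| 10% vs 10% (*f* = 0.5) | 30% | about 71% |
| 10% vs 5% | 28% to 29% | 62% to 71% |
| 15% vs 5% | 25% to 28% | 52% to 66% |
| 20% vs 5% | 22% to 27% | 40% to 62% |

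Equal rates leave the ratio unbiased, because *f*^0 = 1; the small loss of power comes from added variance.

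**No true LOS effect, 20% vs 5%, *f* = 0.5.** Observed ratio = 0.5^(−0.15) = 1.11. The device arm looks 11% longer, and the false rejection rate is about 11% instead of 5%.

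**A different model.** With a Mann-Whitney test, a median of 4 days and exit spread over 20-80% of the stay, a true 30% reduction gives a mean difference of −1.44 days and 73% power without self-discharge, and −1.15 days and 49% at 15% vs 5%. Direction and size are similar.

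**Ranking self-discharge worst.** A Wilcoxon test on that ranking gives 82-90% power for the 30% reduction at 15% vs 5%, 20% vs 5% and 30% vs 10%. In the same three scenarios with no LOS effect it rejects in 12%, 20% and 34% of trials. At 10% in each arm its power is about 54%, against 71% for raw LOS. The competing-event analysis was not simulated.

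**The case against.** The case on the other side has four parts.

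- *No difference between arms is shown.* The background passage describes usual care, where recurrent opioid use and poor analgesia lead to frustration. In this trial both arms may have rescue medication if symptoms persist or if the patient asks, so a failing sham patient has an alternative to leaving. This stands. A reader might infer that the bias, and its direction against the device, follow from the plan's own text. They do not: the text makes unequal self-discharge plausible, but gives no rate for either arm.
- *Modest gaps matter little.* This stands. At 10% vs 5% with exit at 75% of the stay, almost nothing is lost. The null example also needs a device that cuts self-discharge by three quarters yet leaves LOS unchanged.
- *Raw LOS is a legitimate quantity.* The plan treats LOS as a healthcare outcome and mentions costs. For hospital days used, actual days are right however the stay ended. This stands, and is why raw LOS should be kept. Table 1 also takes pain, nausea and vomiting, rescue use and satisfaction at discharge, so an early leaver who is still ill could be partly visible. These measures do not correct the LOS comparison.
- *The worst-rank test looks better than it is.* A reader might take 82-90% power as a reason to replace the endpoint. That power comes partly from the assumed gap in self-discharge, as the 12-34% rejection rates without any LOS effect show. It is a composite, not a sharper test of LOS.

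None of this answers the remaining gap: the plan names self-discharge as a sign of perceived failure and does not provide for identifying it.

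**Conclusion.** The point holds in a conditional form. As written, the plan scores an exit against advice as a short stay. If self-discharge is unequal, LOS is biased in favour of the arm with more of it; if rates and timing are equal, there is no bias. Under the stated assumptions the effect runs from slight (a 30% reduction seen as 28-29% at 10% vs 5%) to substantial (22-27%, with power down from about 74% to 40-62%, at 20% vs 5%). None of these rates comes from the documents, so the table shows sensitivity and is not a forecast.

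The documents do not support saying that the LOS comparison is certainly biased, that the bias must run against the device, or that raw LOS should be dropped. LOS is one of four secondary outcomes in a study that calls itself a pilot, and the primary outcome and sample size are untouched. The change is still worth making, because it is cheap and protects a stated objective against a mechanism that the plan itself describes.

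**What to change.** 1. Record discharge type (routine, against advice, transfer) for every patient, and report self-discharges by arm.
2. Keep raw LOS as the measure of hospital days used.
3. Pre-specify one supportive analysis: time to medically approved discharge, with self-discharge as a competing event, or alternatively a rank test with self-discharge ranked worst. Choose between them before unblinding, and state the start of the clock and how transfers are treated.
4. Draw the LOS conclusion from both analyses. Do not claim a shorter stay as a benefit if it disappears in the supportive one.

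The cost is one data field, one extra analysis and a few sentences in the SAP. The documents do not say whether discharge type is already captured, so the case report form should be checked. The supportive analysis combines LOS with self-discharge and must be described that way. The ranked version also loses power when rates are equal (about 71% to 54% at 10% in each arm), which is a reason to make it supportive and not the only LOS analysis. No change to the sample size is needed.

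### The satisfaction survey is scheduled only at discharge and left out of the existing day-5 outpatient contact, so scores may be missing for reasons tied to satisfaction

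*Combined protocol and SAP*

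**What the plan says.** Satisfaction closes the list of secondary outcomes in the Outcomes paragraph (Methods): "c) hospital LOS and (d) survey on patient satisfaction". It is also part of the second hypothesis in the opening summary and of Objective 1c. On timing, the paragraph says that "LOS and patient satisfaction will be assessed at the time of discharge (Table 1", in contrast to the other outcomes, which are daily.

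Table 1 agrees. The row "Patient Satisfaction Survey" has a single mark, in the Discharge column. The column headed 5 days carries an asterisk, and its footnote reads "questionnaires will be completed as an outpatient if patient is already discharged". In that column the nausea and vomiting index, abdominal pain and the need for opiates and other rescue medication are marked. Satisfaction is not.

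The background section on opioid use in CVS says of this population that "patients even leave against medical advice out of frustration with what they perceive as ineffective care". It gives no rate.

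The Statistical Analysis paragraph has no rule for missing data, and no section says how the survey is obtained from a patient who leaves without completing it.

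**The concern.** A patient who walks out because care seemed ineffective is likely to be dissatisfied, and is plausibly less likely than others to complete a survey on the way out. The reason for the missing value would then be the value itself. Randomization does not protect a comparison restricted to completers when the chance of completing depends on the outcome and differs by arm.

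Length of stay is scheduled for the same moment but does not share the problem, because it can normally be taken from the hospital record. A satisfaction score can come only from the patient, and one not collected near the time may not be recoverable later. What is at stake is the interpretation of a named secondary outcome that supports one of the two stated hypotheses.

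**Working it through.** **1. The plan's own figure.** The Methods section gives "At a significance level of 0.05 and 80% power", a "minimum standardized effect size of 0.64 using two-sided tests", and "we estimate a sample size of 40 participants per group". The normal approximation is n = 2(z₀.₉₇₅ + z₀.₈₀)² / d² = 2(1.960 + 0.842)² / 0.64² = 38.3, rounded up to 39 per group. The two-sample t-test version gives 39.3, rounded up to 40. The stated figure is reproduced. It is not tied to satisfaction, and nothing below changes it.

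**2. The schedule, row by row.**

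| Item in Table 1 | 5 days* (outpatient if already discharged) | Discharge |
|---|---|---|
| Nausea and vomiting index | marked | marked |
| Abdominal pain | marked | marked |
| Opiates and other rescue medication | marked | marked |
| Length of stay | not marked | marked |
| Satisfaction survey | not marked | marked |

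Text and table agree on discharge only. A later contact exists, but as scheduled it does not carry the survey.

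**3. Direction of the bias.** The documents give no rate of missed surveys, so every rate here is an assumption. Let satisfaction be normal with SD 1 in each arm, and suppose the lowest-scoring fraction m of an arm is exactly the part that is missing. This is a worst case for a given m. The mean of those who remain exceeds the true arm mean by

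λ(m) = φ(a) / (1 − m), with a = Φ⁻¹(m).

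The values are:
- λ(0.05) = 0.1031 / 0.95 = 0.109
- λ(0.10) = 0.1755 / 0.90 = 0.195
- λ(0.15) = 0.2332 / 0.85 = 0.274
- λ(0.20) = 0.2800 / 0.80 = 0.350

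The bias in the device-minus-sham difference among completers is λ(m device) − λ(m sham). In this model it does not depend on the true difference.

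| Missing, device | Missing, sham | Bias (SD) |
|---|---|---|
| 5% | 5% | 0 |
| 12% | 12% | 0 |
| 5% | 10% | 0.109 − 0.195 = −0.09 |
| 5% | 15% | 0.109 − 0.274 = −0.17 |
| 5% | 20% | 0.109 − 0.350 = −0.24 |
| 10% | 5% | 0.195 − 0.109 = +0.09 |
| 15% | 5% | 0.274 − 0.109 = +0.17 |

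Equal loss of the lowest scorers cancels. Heavier loss on sham pulls the difference down, and heavier loss on the device pushes it up.

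**4. A milder mechanism.** Suppose that only half of the patients scoring more than 1 SD below the sham mean are lost, and assume a true difference of 0.64 SD purely for illustration. Then 7.9% are missing on sham and 2.5% on the device, and the completers' difference is 0.56 SD, a bias of −0.08. If all such patients are lost (15.8% and 5.1%), it is 0.46 SD, a bias of −0.18.

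**5. Would an imbalance be noticed?** At 40 per group, 15% against 5% is 6 against 2 missing surveys. Fisher's exact test on 6/40 against 2/40 gives p = 0.26. A sensitivity analysis run only when missingness differs significantly by arm would not be triggered, although in the worst case of step 3 the bias would be 0.17 SD.

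**The case against.** The strongest reply is that this is one unmarked cell. The footnote speaks of questionnaires in general, which can be read to include the survey. That makes the wording arguably ambiguous, but the Outcomes paragraph and the empty cell both point to discharge only, and staff following the schedule would have no instruction to collect the survey at day 5. The footnote does rule out a stronger inference, that patients who leave early are never contacted again: a day-5 outpatient contact is planned.

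The harm is also assumed rather than shown. The background describes CVS care generally and says nothing about survey completion. Assessment timed to discharge does not exclude patients who discharge themselves, so not every leaver need be missed. The frustration described concerns poor pain relief, and the Methods section allows rescue medication in both arms, including on request, which may narrow any difference in walk-outs. The only retention figure in the documents is 12% dropout in an earlier neurostimulation trial, described as low, though that trial is not this setting. All of this stands, and it is why no size can be attached to the problem.

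A reader might also infer that the schedule conceals a benefit of the device. The documents do not support that. It would require heavier loss of dissatisfied patients on sham, which is plausible if the device works but not established. Equal loss does no harm in the model above, and the opposite pattern exaggerates the benefit.

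Finally, satisfaction is the last-listed secondary outcome of a study meant to yield preliminary data. That limits the weight of the point but does not remove it, given how little the repair costs.

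**Conclusion.** The point holds as a gap in data collection. Satisfaction is scheduled once, at discharge. It is not included in the outpatient contact that Table 1 already provides, and no rule covers a patient who leaves without completing it. Because the protocol itself describes departures driven by dissatisfaction, the missing scores may depend on the outcome.

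The bias is conditional on loss differing by arm, and its direction depends on which arm loses more dissatisfied patients. Its size is unknown. The shifts of roughly 0.09 to 0.24 SD rest on assumed loss rates, a normal score and the lowest scorers being exactly those missing. They show what could happen and do not estimate what will. The documents name no satisfaction instrument, so these shifts cannot be turned into points on a scale.

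The primary outcomes and the sample size are unaffected. The change is worth making because it lowers the risk of bias in an outcome that carries part of the second hypothesis and of Objective 1c.

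**What to change.** - In Table 1, mark the satisfaction survey in the 5-day column for any patient without a discharge survey, including those who left against advice, and say the same in the Outcomes paragraph.
- Record for each survey whether it was completed at discharge or at day 5.
- Report missing surveys and self-discharges by arm.
- In the Statistical Analysis paragraph, prespecify one sensitivity analysis of satisfaction in which surveys missing after self-discharge are ranked lowest, for example in a rank-based comparison. Run it whatever the observed imbalance, since a significance trigger would have little chance of firing at 40 per group.

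The cost is one mark in a table, one recorded field and one extra analysis, using a contact already planned. Two limits remain. Some surveys will be answered at day 5 rather than at discharge, possibly more often in one arm, which is why the time point should be recorded. Some leavers may still not respond, which is what the sensitivity analysis is for. No change to treatment or sample size follows.
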